## **6.7. Management of Study Drug-Related Events**

### **6.7.1. Temporarily Suspending Treatment Administration**

If a subject meets any of the following conditions within 48 hours prior to the scheduled administration of the trial treatment, treatment administration will be temporarily suspended:

1. To reduce the risk of CRS, subjects will not be given a repeat dose of ELI-002 if they are exhibiting  $T \geq 38^{\circ}\text{C}$  and/or  $\text{IL-6} \geq 500 \text{ pg/mL}$  (cytokine collection, including IL-6, may be performed up to 7 days prior to treatment). In addition, if a subject exhibits  $\text{IFN}\gamma \geq 1000 \text{ pg/mL}$ , the Elicio medical monitor should be contacted for consultation.
2. Adverse event(s) that meet the definition of DLT caused by prior treatment. See [Section 6.7.3](#) for the definition of a DLT; see [Section 12.4](#) for the definition of Common Terminology Criteria for Adverse Events (CTCAEs).
3. Any subsequent dosing in a subject who has experienced Grade  $\geq 2$  CRS/ immune effector cell-associated neurotoxicity syndrome (ICANS)

Investigators must consult the medical monitor to discuss any subjects meeting the above criteria.

In the event the ELI-002 dose is held, the subject should not receive any make up dose and remain on the original protocol schedule (ie, their next dose will be at the next protocol-specified dose if they meet the criteria for dosing). All trial procedures and treatment administration will be resumed as soon as the subject's condition allows or at the investigator's discretion after Sponsor approval.

The trial may proceed at a lower dose, at a less frequent schedule, or omitting the Amph-CpG-7909 adjuvant while continuing to administer the Amph-Peptides, based on emerging toxicity or pharmacodynamic data until the MTD is determined.

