2. Subjects must have recovered from surgery without any ongoing medical/surgical issues. See Inclusion and Exclusion Criteria in [Section 7.1](#) and [Section 7.2](#), respectively.
3. Physical examinations are defined in [Section 12.1.3](#). In addition, a neurological examination for baseline ICANS/ICE assessment will be performed at Visit 3, prior to

dosing.

4. Safety laboratories should include CBC with differential: chemistry to include parameters listed in [Section 12.1.6.3](#); hematology to include parameters listed in [Section 12.1.6.1](#); coagulation to include parameters listed in [Section 12.1.6.2](#). Cytokine laboratories IL-2, IFN $\gamma$ , IL-6, IL-10, and TNF $\alpha$ ; this testing should be performed and reviewed within 7 days prior to dosing. The PBMCs may be used for immunogenicity and/or biomarker genetic sequencing. Details for central laboratory sample collections are provided in the Central Laboratory Manual.
5. ctDNA blood testing will occur at a central laboratory. Details for blood collection are provided in the Central Laboratory Manual
6. High resolution HLA will be performed for all subjects, prior to first dose at Visit 3. Cohorts will be enrolled regardless of the HLA subtype (see [Section 6.1.3](#) for details). Details for blood collection are provided in the Central Laboratory Manual.
7. ELI-002 administration: Subjects will receive the initial dose of ELI-002 and be monitored for  $\geq 24$  hours in order to monitor for potential adverse events such as CRS. For subsequent doses, subjects must be observed for safety for at least 1-hour postdose.
8. Check for signs of toxicity. See [Section 6.7](#) for instructions regarding signs of toxicity and for criteria for stopping treatment administration.
9. Subjects will be provided with a paper reactogenicity diary at the end of the visit. They will be instructed to fill out the diary each day, for 7 days, at the same time per the instructions on the study template. Subjects will return the completed diary at the next scheduled visit. The site staff will review the diary with the subject and file in the subject study records. This completed diary will be used as source data for eCRF data entry.

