## 6.8. Management of Risks and Toxicities

Review of the ELI-002 pre-clinical data indicates that certain cytokine levels such as IL-6 may be elevated (see Section 4.4). Elevated cytokines are a hallmark of CAR-T cell therapies often leading to CRS and ICANS which can be serious or fatal.

Consequently, the management of such toxicities have been extensively reviewed through the CAR-T Toxicity Management Workgroup [Lee et al, 2019]. To be fully prepared in the event that CRS is observed, this trial will follow the same guidelines as are used for CAR-T studies as outlined in Section 6.8.1 through Section 6.8.2.

All subjects will be monitored for potential AEs such as CRS. In addition, there will be a 1-week stagger between enrollment of the first subject in a cohort and the subsequent subjects. In addition, all patients will be asked to stay within one hour travel time to the clinic for at least 24 hours following their first ELI-002 dose.

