### 6.8.1. Management of Cytokine Release Syndrome

Since ELI-002 activates T cells by a novel amphiphile mechanism whereby potent responses are generated, there is a theoretical risk for observation of T-cell-mediated toxicity.

To reduce the risk of CRS, subjects will not be given a repeat dose of ELI-002 if they are exhibiting  $T > 38^{\circ}\text{C}$  and/or  $\text{IL-6} > 500 \text{ pg/mL}$ . In addition, if a subject exhibits  $\text{IFN}\gamma \geq 1000 \text{ pg/mL}$ , the Elicio medical monitor should be contacted for consultation.

In the event the ELI-002 dose is held, the subject should not receive any make up dose and remain on the original protocol schedule (ie, their next dose will be at the next protocol-specified dose if they meet the criteria for dosing and with approval from the medical monitor).

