Cytokine release syndrome is caused by the release of inflammatory cytokines such as IL-6, IL-2,  $\text{IFN}\gamma$ , and  $\text{TNF}\alpha$ , which causes a systemic inflammatory response similar to sepsis. The release of cytokines occurs when cells that are targeted by antibodies, immune effector cells (T and B-cells, Natural Killer cells, and monocytes/macrophages) are recruited to the tumor area and the subject's immune cells are activated. The importance of cytokine secretion of CAR T cells after exposure to tumor cells is closely related to their killing activity, and the degree of cytokine elevation is correlated to the bulk of residual disease at the time of adoptive T-cell infusion, ie, tumor burden, as well as with the number of detectable CAR T-cells after administration [Brentjens, 2012; Lee et al, 2015, Lee et al, 2019]. IL-6 levels in patients with low grade 0-3 CRS were a median of 100 pg/mL, whereas IL-6 was a median of 10,000 pg/mL [Teachey et al, 2016] in patients with high grade 4-5 CRS. Likewise,  $\text{IFN}\gamma$  was approximately 40 pg/mL in patients with low grade CRS, versus approximately 4,000 pg/mL in those with high grade CRS [Teachey et al, 2016]; therefore, this protocol takes a conservative cut-point and mandates dose hold for ELI-002 if  $\text{IL-6} > 500 \text{ pg/mL}$  is observed or contact with the medical monitor in the event that  $\text{IFN}\gamma > 1000 \text{ pg/mL}$  is observed, making the assumption that although CRS guidelines address CAR-T safety management, ELI-002 may elicit sufficient T cells to merit a similar approach. The goal of CRS management is to prevent life-threatening complications while preserving the antitumor T cell immune response.

Clinical signs and symptoms of CRS listed in [Table 17](#) should raise concern.

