## 10.2. Immunization Period

During the Immunization Period, subjects will receive 4 weekly SC injections (Weeks 1 to 4) followed by 2 injections at Week 6 and Week 8 (Table 12). If the subject has fever  $\geq 38.0^{\circ}\text{C}$  and/or elevated IL-6  $\geq 500$  pg/mL, proceed with the visit but omit study treatment administration; if fever abates and cytokines diminish to  $< 500$  pg/mL, the subject may proceed with the next scheduled dose after approval from the medical monitor). In addition, if a subject exhibits IFN $\gamma$   $\geq 1000$  pg/mL, the Elicio medical monitor should be contacted for consultation.

All laboratory samples should be taken prior to dosing on any study visit that has dosing.

At **Visit 3 (Baseline, Day 57) prior to trial drug administration**, the following visit procedures will include:

- Administer the EORTC QLQ-C30 and the tumor type-specific PRO (see Section 11.3).
- Record any change in medical history since the previous visit. Subjects must have recovered from surgery without any ongoing medical/surgical issues.
- Record any change in cancer history since the previous visit.
- Perform a physical examination which will be based on institution standard of care (see Section 12.1.3). In addition, a neurological examination for baseline assessment of ICANS/ICE will be performed.
- Record vital signs (blood pressure, pulse rate, body temperature, and respiratory rate).
- Record weight.
- Perform a 12-lead ECG (to be reviewed by a cardiologist or clinical investigator according to institutional guidelines and practice).
- Confirm ECOG Scale of Performance Status is 0 or 1.
- Record any change in concomitant medications since the previous visit.
- Collect a blood sample for clinical laboratory assessments, including the cytokine panel (local laboratory; see Section 11.1 and Section 12.1.6). Note: cytokine testing should be performed within 7 days prior to dosing.
- Collect a blood sample for ctDNA (to be performed at a central laboratory).
- Collect a blood sample for high resolution HLA typing (central laboratory).
- Record any pre-treatment SAEs that have occurred since the previous visit.

**Dose 1:** The first dose must be administered at the clinical site. Subjects must be observed by study staff for at least 1-hour postdose for observation and must stay within an hour of the clinic for  $\geq 24$  hours in order to monitor for potential AEs such as CRS.

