**After dose administration** the following visit procedures will occur:

- Record vital signs (blood pressure, pulse rate, body temperature, and respiratory rate). Measurements will be obtained after 3 minutes in the sitting position. No other measurements or procedures were performed during this 3-minute period.
- Subjects will be provided with the reactogenicity diary to complete for 7-days following the dose. Subjects will be instructed how to complete the diary and to return the completed form at their next visit.

At **Visit 4 (Day 64)**, the following visit procedures will include:

- Administer the EORTC QLQ-C30 and the tumor type-specific PRO (see [Section 11.3](#)).
- Perform a physical examination, which will be based on institution standard of care (see [Section 12.1.3](#)).
- Record vital signs (blood pressure, pulse rate, body temperature, and respiratory rate). Measurements will be obtained after 3 minutes in the sitting position. No other measurements or procedures were performed during this 3-minute period.
- Record weight.
- Confirm ECOG Scale of Performance Status.
- Record any change in concomitant medications since the previous visit.
- All laboratory samples should be taken prior to dosing on any study visit that has dosing.
  - Collect a blood sample for clinical laboratory assessments, including the cytokine panel (local laboratory; see [Section 11.1](#) and [Section 12.1.6](#)). Note: cytokine testing should be performed and reviewed within 7 days prior to dosing.
- Record any AEs since last visit. Check for signs of toxicity. Including fever, and laboratory evidence of elevated cytokines. Hold the ELI-002 dose if Grade  $\geq 2$  CRS is present, or if elevated cytokine IL-6 is present. If elevated IFN $\gamma$  is present, the Elicio medical monitor should be contacted for consultation([Section 6.8.1](#)).
- **Dose 2:** Trial drug administration and subjects must be observed by study staff for at least 1-hour postdose for observation.
- Subjects will be provided with the reactogenicity diary to complete for 7-days following the dose. Subjects will be instructed how to complete the diary and to return the completed form at their next visit.

At **Visit 5 (Day 71)**, the following visit procedures will include:

- Administer the EORTC QLQ-C30 and the tumor type-specific PRO (see [Section 11.3](#)).
- Perform a physical examination, which will be based on institution standard of care (see [Section 12.1.3](#)).

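### The 7-day allowance lets the IL-6 sample that clears a weekly repeat dose be drawn before the preceding dose (Doses 2, 3, 4, 8, 9 and 10)

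*Protocol*

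**What the plan says.** Section 6.7.1 lists the conditions that suspend a dose. For CRS risk, a repeat dose is withheld at a temperature of 38 °C or above and/or IL-6 of 500 pg/mL or above. The section opens with a 48-hour look-back, but a parenthesis relaxes it for cytokines: "cytokine collection, including IL-6, may be performed up to 7 days prior to treatment".

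The allowance is repeated in the schedules. Table 12 footnote 4 and Table 14 footnote 3 both say that "this testing should be performed and reviewed within 7 days prior to dosing". The dosing-visit text in 10.2 and 10.4 carries a matching note: "cytokine testing should be performed and reviewed within 7 days prior to dosing".

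Three other provisions bear on the point:

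- Section 10.2, and the visit lists in 10.4: "All laboratory samples should be taken prior to dosing on any study visit that has dosing".
- Each repeat-dose visit says to hold for Grade 2 or higher CRS "or if elevated cytokine IL-6 is present".
- Section 6.8 gives the reason for the monitoring: "Review of the ELI-002 pre-clinical data indicates that certain cytokine levels such as IL-6 may be elevated". Section 6.8.1 makes the hold compulsory: "this protocol takes a conservative cut-point and mandates dose hold for ELI-002 if" IL-6 exceeds 500 pg/mL.

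**The concern.** The IL-6 rule is meant to stop a further dose in a subject whose cytokines rose after the last one. It can do that only if the sample was drawn after that last dose. With weekly dosing, a 7-day look-back reaches to the day of the preceding dose, and further back if the visit windows shorten the gap. The sample on file from the preceding visit was drawn before that visit's injection, so it says nothing about what the injection did.

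The other holds cover most subjects with clinical signs: fever, Grade 2 or higher CRS/ICANS, and events meeting the DLT definition. They do not cover an afebrile subject with isolated IL-6 elevation, because DLT criterion (a) in 6.7.3 excludes asymptomatic laboratory abnormalities. Only the IL-6 criterion catches this subject, and as written a site could give the next dose while following the protocol. The trial is first-in-human, and the SAP (Section 8.1) adds cohorts at 5.0 and 10.0 mg Amph-CpG-7909, above the three planned levels.

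**Working it through.** **Inputs.** Dose days from Tables 12 and 14: 57, 64, 71, 78, 92, 106 (Doses 1 to 6) and 196, 203, 210, 217 (Doses 7 to 10), each ±3 days. Look-back allowance: 7 days (6.7.1). Sample position at a dosing visit: before the dose (10.2, 10.4).

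**Step 1: nominal gaps.** Successive differences for Doses 2 to 10 are 7, 7, 7, 14, 14, 90, 7, 7 and 7 days. This reproduces the pattern in Section 6.1: four weekly doses, two at two-week intervals, then four weekly boosters. Six of the nine repeat doses have a 7-day nominal gap.

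**Step 2: gaps allowed by the windows.** If the current dose moves by *a* days and the preceding one by *b* days, each from −3 to +3, then

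gap = nominal gap + (*a* − *b*),

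with 7 × 7 = 49 combinations per pair, and *a* − *b* running from −6 to +6.

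| Doses | Nominal gap | Permitted range | Under 7 days | Exactly 7 | Over 7 |
|---|---|---|---|---|---|
| 2, 3, 4, 8, 9, 10 | 7 | 1 to 13 | 21/49 | 7/49 | 21/49 |
| 5, 6 | 14 | 8 to 20 | 0/49 | 0/49 | 49/49 |
| 7 | 90 | 84 to 96 | 0/49 | 0/49 | 49/49 |

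**Step 3: where the look-back lands.** The earliest permitted sample falls at (gap − 7) days relative to the preceding dose.

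- Gap of 7 days: 7 − 7 = 0, the day of the preceding dose. That visit's sample was drawn pre-dose, so it precedes the injection. Whether it is still within 7 days depends on how days are counted, hence a boundary case.
- Gap of 6 days: 6 − 7 = −1. Gap of 1 day: 1 − 7 = −6. The look-back reaches 1 to 6 days before the preceding dose, so the earlier pre-dose sample clearly qualifies.
- Gap over 7 days: the earliest permitted sample falls after the preceding dose, so there is no problem.

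**Step 4: is the gap closed elsewhere?** No provision requires the qualifying sample to follow the preceding dose, and none sets a minimum interval between doses. Cytokines are run at local laboratories (6.1) with no stated turnaround, and Table 12 schedules no cytokine draw between dosing visits. Where results are not available the same day, the newest scheduled result at the time of dosing may therefore be the previous visit's pre-dose sample.

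**The case against.** The best reply is that the 7-day note belongs to each visit's own panel. Tables 12 and 14 mark a separate cytokine collection at every dosing visit, and the note sits within that visit's collection instruction. On this reading, Visit 3's sample is Visit 3's test. Clearing Dose 2 on it would mean omitting Visit 4's panel or dosing without reviewing it. The hold language also concerns current status: 6.7.1 has a 48-hour lead-in, and resumption requires IL-6 to have fallen below 500 pg/mL. Very short gaps fit poorly with dosing described as weekly and a diary kept for 7 days after each dose.

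Part of this stands. A site that draws and reviews the panel at the visit gates on post-dose data. Gaps near 1 day are not what the authors intended, and the 49 combinations should not be read as likelihoods.

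It does not close the gap. Even if the note attaches to each visit's own panel, that panel may be drawn up to 7 days early, and so before the preceding dose when the gap is 7 days or less. The 48-hour lead-in is expressly relaxed for cytokines. The instruction to hold for elevated IL-6 does not identify the sample, and the same visit text carries the 7-day note. Neither the weekly description nor the diary sets a minimum interval.

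**Conclusion.** The concern holds. For six of the nine repeat doses, the protocol permits the mandatory IL-6 check to be met by a sample that cannot show the effect of the preceding dose: clearly in 21 of 49 permitted timings, and at the boundary in a further 7. Doses 5, 6 and 7 cannot be affected under any permitted timing.

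The counts assume that the two visit windows move independently and that no unstated minimum interval applies. The exposed case is narrow: IL-6 of 500 pg/mL or more with no fever, no Grade 2 or higher CRS/ICANS and no DLT-type event. The documents give neither an assay turnaround nor an IL-6 time course after dosing, so its frequency cannot be estimated. It should be fixed because a compulsory safety rule can be satisfied without testing what it is meant to test, and the correction is cheap.

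**What to change.** In Section 6.7.1, Table 12 footnote 4, Table 14 footnote 3 and the visit text of 10.2 and 10.4, state:

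> The IL-6 sample that qualifies a repeat dose must be drawn after the preceding ELI-002 dose and within 7 days before the planned dose, with the result reviewed before dosing.

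As a minor alignment, the rule in 6.8.1 beginning "To reduce the risk of CRS, subjects will not be given a repeat dose of ELI-002 if they are exhibiting" uses strict inequalities (above 38 °C, above 500 pg/mL), whereas 6.7.1, 10.2 and 10.4 include the thresholds themselves. Use ≥38 °C and ≥500 pg/mL throughout.

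The cost is protocol wording only, since a cytokine panel is already scheduled at every dosing visit. Sites without same-day results may have to draw the sample a few days before the visit, or dose later in the window when the gap is very short. If dosing in this trial is finished, the sentence should go into any later protocol that reuses the rule; an extension with further dosing is foreseen in 6.1.2 and 12.8.

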### **6.7.2. Permanent Stopping Treatment Administration**

If a subject meets any of the following conditions, the subject will be required to discontinue the trial treatment administration but should continue other trial-related procedures as specified for the follow-up period of the study. (See [Section 7.3](#) for more information on procedures for subjects withdrawn from trial treatment.)

1. Evidence of radiographic disease progression
2. Any intolerable AE, at the investigator's discretion

3. During study treatment:
  - Any investigational product use other than ELI-002
  - Other anti-cancer treatment
4. Non-compliance with trial treatments/procedures. If a subject misses  $\geq 2$  trial visits without underlying toxicity, the subject should be re-instructed regarding dosing and follow-up and continue trial participation. If a subject continues to miss trial visits without toxicity and despite re-instruction, they should be discontinued from the trial treatment phase but follow-up data should be collected as possible.
5. The subject requests to be withdrawn from the trial treatment

For subjects whose treatment is discontinued prematurely, the procedures outlined for End of Treatment/Visit 15 (Table 14) will be carried out and, if possible, prior to the initiation of any other anti-cancer treatment. These subjects should then enter the Follow-up Period, where procedures listed in Table 15 and Table 16 will be performed. In the event that a subject will not continue to be evaluated in the Follow-up Period, the End of Study visit (Visit 24) should be scheduled, and all procedures performed.

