The RP2D will be defined in consideration of the MTD (if any), safety data, and pharmacodynamic data. The RP2D will be communicated to all sites in a trial memo following the last SMC cohort review.

Subject replacement: If a subject discontinues for any reason other than toxicity prior to completing 28 days of ELI-002 therapy, a replacement subject will be added to the cohort until 3 subjects per cohort complete 28 days of ELI-002 therapy.

DLT definition: A DLT will be defined as any event at least possibly related to ELI-002 as follows:

- a. Any Grade  $\geq 3$  non-hematologic toxicity except asymptomatic laboratory abnormalities (see Section 12.2.1.1)
- b. Any Grade  $\geq 3$  toxicity involving major organ systems for greater than 72 hours and occurring within 28 days of subcutaneous administration
- c. Grade 3 CRS that does not resolve to  $\leq$  Grade 2 within 7 days
- d. Any Grade 4 CRS that does not improve to  $<$  Grade 2 within 72 hours
- e. Any Grade  $\geq 3$  autoimmune disorder
- f. Any Grade  $\geq 3$  rash that does not resolve to  $\leq$  Grade 1 within 7 days with appropriate treatment

The DLT observation period will be 28 days.

MTD definition: The MTD is defined as the highest dose level with a DLT incidence  $<33\%$  of cohort subjects.

The trial will consist of a Screening Period, an Immunization Period, a No Dosing 3-Month Period, a Booster Period, and a Follow-up Period.

A Booster Period is provided as further lymph node antigen exposure may be required to maintain effective levels of antigen-specific T-cells. All subjects will receive booster doses unless they have unresolved toxicity.

All subjects will be observed for safety and tolerability. CT imaging with contrast will occur at screening and 35 days post first dose and at additional timepoints until radiographic relapse is observed.

The central laboratory will confirm  $\geq 1$  of 2 mutant KRAS/NRAS alleles targeted by ELI-002 Amph-Peptides 2P (G12D, and G12R,) is present and central laboratory ctDNA must be positive or there must be serum tumor biomarker (such as CA19-9, CEA, and CA-125) elevation at  $\geq 21$  days post-surgery or after last administration of adjuvant therapy (whichever comes last in the specific subject treatment plan). These data are required for determination of eligibility and inclusion into the trial.

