Immunologic biomarkers of response may include HLA typing, serum cytokines, ICS, Fluorospot, and/or dextramer+ T cells for subjects with appropriate HLA alleles will be determined when matching dextramer/s is/are available.

Local laboratories will be utilized for serum cytokine testing, tumor biomarkers CA19-9/CEA/CA-125, tumor biopsy assays (such as biomarker sequencing and/or IHC assays) and all other safety laboratory tests.

[figure not shown]
Central laboratories will be utilized for ctDNA analysis, HLA typing, PBMC isolation and immunogenicity assessment, such as Fluorospot, ICS, and/or T cell dextramer testing as detailed in the central laboratory manual.

While HLA testing will be performed prior to first dose at Visit 3, cohorts will be enrolled regardless of the subject HLA subtype.

**Discontinuation of trial treatment:** Subjects with confirmed radiographic relapse (using iRECIST criteria; not judged as pseudoprogression) during treatment with ELI-002 will discontinue trial treatment but should continue other trial-related procedures in the follow-up period. The ORR using iRECIST criteria will be characterized for any cross-over subjects.

[figure not shown]
The design of the trial is outlined in [Figure 2](#) and [Figure 3](#).

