### **6.1.2. Criteria for Booster and Additional Booster Vaccines**

Accumulating clinical evidence indicates some subjects treated with an immunotherapy, such as ELI-002, may be assessed as having disease progression by conventional response criteria before demonstrating clinical objective responses and/or stable disease [[Wolchok et al, 2009](#)]. This pseudoprogression has been observed in the ELI-002-001 trial. Two hypotheses have been suggested to explain this phenomenon. The first is that enhanced inflammation within the lesions could lead to an increase in the lesion size which would appear as enlarged index lesions and therefore as newly visible small non-index lesions. Over time, both the malignant and inflammatory portions of the lesion(s) may then decrease leading to overt signs of clinical improvement. The second hypothesis is that, in some subjects, the speed of the lesion growth may initially outpace the anti-tumor immune activity of the therapy. With sufficient time, the anti-tumor activity will dominate and become clinically apparent. Therefore, subjects participating on ELI-002-001 will be allowed to continue ELI-002 treatment, as specified in this protocol, after initial investigator assessed progression (iUPD via iRECIST) if the subject is deriving clinical benefit and tolerating the study treatment well in the judgement of the investigator. Subjects must discontinue treatment upon confirmed disease progression.

All subjects free of confirmed radiographic progression will receive booster doses unless they have unresolved toxicity. For subjects which have encountered signs of toxicity, the investigator must consult with the sponsor's medical monitor who must agree with resuming the subsequent booster vaccinations (see [Section 6.7.1](#)).

Subjects who remain in the trial until the end of the required Follow-up Period may be eligible to enroll in a separate extension protocol to continue to receive further lymph node antigen exposure to maintain effective levels of antigen-specific T-cells.

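### Section 6.7.2 stops ELI-002 at any radiographic progression, while 6.1.2, 6.1 and the synopsis stop it only at confirmed progression, and no scheduled scan can confirm a Visit 10 finding before the boosters

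*Protocol*

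**What the plan says.** Protocol Section 6.7.2 lists conditions under which "the subject will be required to discontinue the trial treatment administration". The first is "1. Evidence of radiographic disease progression". It does not mention confirmation, pseudoprogression or iUPD.

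Protocol Section 6.1.2, which sets the booster criteria, takes a different line. It discusses pseudoprogression, reports that it has been seen in this trial, and allows treatment to continue "after initial investigator assessed progression (iUPD via iRECIST) if the subject is deriving clinical benefit and tolerating the study treatment well". It then says "Subjects must discontinue treatment upon confirmed disease progression", and on boosters: "All subjects free of confirmed radiographic progression will receive booster doses unless they have unresolved toxicity".

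Protocol Section 6.1 agrees with 6.1.2: "Subjects with confirmed radiographic relapse (using iRECIST criteria; not judged as pseudoprogression) during treatment with ELI-002 will discontinue trial treatment". The synopsis repeats that paragraph under discontinuation of trial treatment. Earlier in the synopsis, however, the booster sentence has no progression exception: "All subjects will receive booster doses unless they have unresolved toxicity".

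On imaging, Table 12 (immunization) and Table 14 (boosters) have no CT row. Table 13 places one CT at Visit 10, and Table 15 places the next at Visit 17. Section 10 matches these tables. The synopsis also names a CT 35 days after the first dose, which none of the schedule tables contains.

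SAP Table 16 counts confirmed progression (iCPD) or death as the RFS event and treats an iUPD scan as one without documented recurrence.

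**The concern.** A subject whose Visit 10 scan shows iUPD, who is benefiting and has no unresolved toxicity, must stop under 6.7.2 and is boosted under 6.1.2. Both instructions are firm. Whether that subject gets four more doses then depends on which section the site consults.

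Exposure, dose intensity and booster-period safety and immunogenicity data could therefore differ between sites for reasons unrelated to dose level. In some subjects the exploratory RFS outcome could differ too. Because the protocol reports that pseudoprogression has already occurred in this trial, the situation is a practical one.

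**Working it through.** The plan gives no figure to reproduce here. The check compares the texts, then does date arithmetic on the schedule, then sets a rough size.

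**Can the texts be read together?** Section 6.1.2 separates initial from confirmed progression, so the missing qualifier in 6.7.2 changes the meaning. No sentence says which section prevails. The reference from 6.1.2 to Section 6.7 is to 6.7.1, and it concerns toxicity. The adverse-event footnotes of Tables 12 and 14 send sites to Section 6.7 for the criteria for stopping treatment. A site working from the booster table therefore reaches 6.7.2, and a site reading the booster criteria reaches the opposite rule.

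**Dates** (Tables 12 to 15; imaging window ±14 days, dosing visits ±3 days)

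- First dose: Day 57. Visit 10 CT: Day 148. Boosters: Days 196, 203, 210 and 217. Visit 17 CT: Day 259.
- Visit 10 CT to first booster: 196 − 148 = 48 days. With windows, 193 − 162 = 31 to 199 − 134 = 65 days.
- Visit 10 CT to Visit 17 CT: 259 − 148 = 111 days. With windows, 245 − 162 = 83 to 273 − 134 = 139 days.
- Earliest Visit 17 CT: 259 − 14 = Day 245. Latest last booster: 217 + 3 = Day 220.

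Even at the window limits, no scheduled scan falls between Visit 10 and the last booster. Confirmation in that interval could come only from an optional biopsy of new lesions or from an unscheduled scan prompted by clinical signs.

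The synopsis CT would fall on Day 57 + 35 = Day 92, which is 56 days before Day 148. If it is done, Day 148 could confirm a Day 92 finding. It could not confirm progression first seen on Day 148.

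**Doses.** Table 12 gives 6 doses and Table 14 gives 4. The same subject receives 6 doses under 6.7.2 and up to 10 under 6.1.2.

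**RFS** (SAP Section 13.6.2 formula and Table 16, scans on nominal days)

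- Stopped at Visit 10, other therapy started, no later iCPD or death: censored under the primary rules at the last scan before that therapy, (148 − 57 + 1)/30.4375 = 3.0 months.
- Confirmed at Visit 17 with no new therapy: event at (259 − 57 + 1)/30.4375 = 6.7 months, whether the subject was boosted or stopped.
- A stopped subject might also be placed in the Table 16 row for discontinuation for undocumented progression, which censors at the last scan without documented recurrence.

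**Size.** Assume exponential relapse times counted from Dose 1. The proportion relapsed by Visit 10, 148 − 57 = 91 days later, is 1 − exp(−ln 2 × 91/median).

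- Median 5 months (Section 4.6.4, pancreatic subjects with persistent ctDNA): 5 × 30.4375 = 152.2 days, giving 34%.
- Median 10.4 months (Section 4.1.1, pancreatic cancer with CA19-9 above normal after adjuvant chemotherapy): 10.4 × 30.4375 = 316.6 days, giving 18%.

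Of 18 planned subjects that is 0.34 × 18 = 6.1 to 0.18 × 18 = 3.2, or about 3 to 6.

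**DLT and MTD.** The DLT window closes 28 days after the first dose, on about Day 57 + 28 = Day 85, before Visit 10.

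**The case against.** The best defence is that item 1 of 6.7.2 is a terse list entry set against three consistent statements elsewhere, one of them in the section written for the booster decision. On that view a sensible site would read confirmation into 6.7.2. The synopsis booster sentence is likewise completed by the discontinuation paragraph later in the same synopsis, so on its own it is weak evidence of conflict. Routes to confirmation also exist through biopsy and unscheduled imaging. All of this lowers the likely number of misapplied decisions. It does not remove the conflict, because 6.7.2 is mandatory, nothing subordinates it, and the dosing tables point to it.

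Three stronger readings are tempting, and the documents do not support them.

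- A reader might infer that Visit 10 is the only planned post-dose scan before the boosters. That is true of the schedule tables and Section 10 but not of the synopsis, which names the Day 92 scan.
- A reader might infer that every disputed subject is either censored at 3.0 months or an event at 6.7 months. Section 6.7.2 sends stopped subjects into follow-up, which includes the Visit 17 CT, so a stopped subject confirmed there without new therapy can have the same event date as a boosted one. Table 16 also labels as events a death or iCPD within 182 days of starting other therapy. The difference arises only in the particular cases listed above.
- A reader might take 34% as the share of subjects affected. That median belongs to ctDNA-positive pancreatic subjects, while the trial also enrols other tumours and subjects eligible on serum markers alone. The calculation also counts every relapse by Day 148, including those confirmed by biopsy or unscheduled imaging and those without the benefit and tolerability that 6.1.2 requires for continuing.

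**Conclusion.** The contradiction stands: a mandatory stopping rule in 6.7.2 conflicts with 6.1.2, 6.1 and the synopsis. For progression first seen at Visit 10, the schedule tables offer no scheduled scan that could settle the matter before the boosters. The firm consequence is exposure of 6 or up to 10 doses according to the section followed. The effect on RFS is conditional and falls on an exploratory endpoint.

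The 18% to 34% range is an upper bound on the disputed group so far as that group consists of true relapse. It rests on an exponential model, on medians borrowed from pancreatic cohorts, and on counting time from Dose 1. Pseudoprogression would add cases, and the documents give no rate for it.

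This should be fixed but falls short of a must-fix. DLT and MTD assessment is untouched, planned enrolment ended in 2Q2023, and the SAP records early termination of long-term follow-up, so few or no subjects may still be due a booster. Its main remaining value is in interpreting the final exposure and RFS results. Nothing here says which stopping criterion is right.

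**What to change.** Reconcile item 1 of Protocol Section 6.7.2 with Sections 6.1.2 and 6.1 and with both synopsis statements (discontinuation and boosters), so that one stopping criterion, in one set of iRECIST terms, appears throughout. The sponsor and SMC decide which criterion applies. Reconcile the synopsis CT at 35 days after the first dose with Table 12.

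For subjects already treated, record whether iUPD or iCPD ended treatment, and report exposure and RFS with that classification.

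The cost is a wording amendment or a clarification memo to sites, one data item on the eCRF, and a classification in the final outputs. No additional patients are needed.
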